4.1.3 MASKING

There will be no masking in this study. Masking of the Study investigators is not possible as they need to measure the study main variables in the predetermined randomized eye.

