2 OBJECTIVES

The primary objectives of this study are:

To compare baseline data between 3 groups - *habitual wearers of DDSH / habitual wearers of DDH / non-lens wearers* - in terms of:

- Limbal & bulbar redness

- Corneal vessel ingrowth

And to compare data post closed eye lens wear in 2 groups - *habitual wearers of DDSH / habitual wearers of DDH* - in terms of:

- Limbal & bulbar redness

The primary study measures are:

- Limbal & bulbar redness (Oculus Keratograph 5)
- Corneal vessel ingrowth (slit-lamp photography & image analysis)

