3 HYPOTHESIS

The study main hypotheses are:

- 1) There will be greater corneal vessel ingrowth in habitual wearers of DDH than DDSH and non-lens wearers at baseline.
- 2) There will be greater limbal & bulbar hyperemia response following 3 hours of wearing a low Dk HEMA CL in habitual wearers of DDH than DDSH and non-lens wearers.

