The first study day will be observational in nature for collecting comparison data across all 3 participant groups described above. There will be only one study visit on day 1.

Visit 0: This visit includes screening, confirmation of CL history, measurements of [REDACTED]

[REDACTED], slit-lamp biomicroscopy, [REDACTED]

[REDACTED]

[REDACTED] Then Day1 exit slit-lamp biomicroscopy [REDACTED]

[REDACTED]

Study Day 2

Only the study groups 1 & 2 will be involved in the second day of study. They will attend the study visit 1 on day 2 at 3 ± 0.5 hours after waking and eye opening in the morning, and wearing their habitual spectacles.

[REDACTED]
[REDACTED]
[REDACTED] [REDACTED]
[REDACTED]
[REDACTED]
[REDACTED]

Visit 2:

[REDACTED]
[REDACTED]
[REDACTED]
[REDACTED] [REDACTED]
[REDACTED]
[REDACTED]
[REDACTED]

Visit 4: 1hr after CL removal

[REDACTED] [REDACTED]
[REDACTED]
[REDACTED]
[REDACTED]

Visit 6: 3hr after CL removal

[REDACTED] the objective ocular
redness measurement OU [REDACTED]

Exit Visit:

[REDACTED]

Biomicroscopy including corneal staining, OU

Study exit [REDACTED]

Exit the study.

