4.1.2 RANDOMIZATION

A randomization schedule will be generated using SAS or a web-based program: (www.randomization.com). The final study randomization schedule will be generated by CORE's Data Management Team, and provided to the research assistants and clinical investigators at each study site for use during the study.

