4.7 STUDY POPULATION

4.7.1 NUMBER OF PARTICIPANTS

Up to a maximum of 26 participants in each study group will be randomized, with a target of completing 17 in each of the three groups.

Groups 1 and 2 will be recruited at both CORE (Canada) and Eurolens (UK). These participants will be exposed to the study contact lens on the second day of the study. There will be competitive recruitment between the two sites and though unlikely, depending on recruitment progress, it is possible that all the subjects will be seen only at CORE (Canada) or only at Eurolens (UK). This means that a maximum of 52 and a minimum of 0 participants will be exposed to the study contact lens at each site.

Group 3, the non-lens wearing group, will all be recruited at CORE (Canada). These participants will only attend the first study visit/day and will not be exposed to the study contact lens.

Participants will be recruited using the study site records and advertising approved by the respective Office of Research Ethics (ORE). Each participant will be given a unique study specific ID number. Additionally, all participants must meet all the study inclusion and none of the exclusion criteria listed below.

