4.7.2 INCLUSION AND EXCLUSION CRITERIA

A person is eligible for inclusion in the study if he/she:

1. Is between 17 and 60 years of age inclusive (age matching required between all 3 study groups), and has full legal capacity to volunteer;
2. Has had a self-reported oculo-visual examination in the last two years.
3. Has read and signed an information consent letter;
4. Is willing and able to follow instructions and maintain the appointment schedule;

5. No previous history of overnight contact lens wear or PMMA (polymethylmethacrylate) lens wear.
6. Auto-refraction vertexed spherical equivalent between +4.00 and -8.00 (prescription matching required between groups 1 & 2). This criterion is non-applicable to participants in group 3.
7. Is found to be in one of the study groups matched by age (± 5 years), ethnicity (Asian vs. non-Asian) and CL Rx (± 2.00 D) according using the following criteria:

GROUP 1: For the past (minimum) 6 months has ONLY worn spherical DDSH lenses AND prior to wearing this lens they only wore SH material lenses in the past (minimum) 3 total years.

GROUP 2: For the past (minimum) 6 months has ONLY worn spherical DDH lenses AND prior to wearing this lens they only wore H material lenses in the past (minimum) 3 total years.

GROUP 3: No previous experience of contact lens wear (no need to match Rx of this group).

8. For groups 1 & 2, currently and for at least the previous 6 months has had habitual daily disposable wear schedule of at least 8 hrs a day, 5 days a week in only one material category - either silicone hydrogel or hydrogel material. This criterion is not-applicable to participants in group 3.
9. Is willing to wear the study contact lens in the randomized eye for 3 hours of eye closure on the second study day. This criterion is not-applicable to participants in group 3.
10. Has clear and healthy corneas and anterior eye and no active* ocular disease;
11. Can achieve monocular HCVA of logMAR 0.10 or better in each eye with subjective refraction or pinhole.
12. Can achieve acceptable fit and comfort in the randomized eye with the study lens. This criterion will be confirmed at the baseline visit (V1). This criterion is not-applicable to participants in group 3.
13. Has a wearable pair of spectacles.

A person will be excluded from the study if he/she:

1. Is participating in any concurrent clinical trial;
2. Is unable/unwilling to provide permission for the study site to seek CL history from their eye care practitioner

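### Section 4.1.3 rules out all masking because of the randomized eye, but that reason does not cover reading the Visit 0 images for vessel ingrowth, a primary measure

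*Combined protocol and SAP*

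**What the plan says.** Section 4.1.3 is unqualified: "There will be no masking in this study". Its only reason is "Masking of the Study investigators is not possible as they need to measure the study main variables in the predetermined randomized eye". Section 4.1.1 likewise labels the study non-masked.

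Section 2 lists among the primary study measures "Corneal vessel ingrowth (slit-lamp photography & image analysis", and names vessel ingrowth in the baseline comparison of the three groups. Section 3 gives it a direction: "There will be greater corneal vessel ingrowth in habitual wearers of DDH than DDSH and non-lens wearers at baseline".

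On Day 1, section 4.1.1 says: "The first study day will be observational in nature for collecting comparison data across all 3 participant groups described above". Section 4.7.1 adds: "Group 3, the non-lens wearing group, will all be recruited at CORE (Canada). These participants will only attend the first study visit/day". The role of the randomized eye appears in the eligibility criteria (4.7.2, criterion 9): "Is willing to wear the study contact lens in the randomized eye for 3 hours of eye closure on the second study day".

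**The concern.** The reason given in 4.1.3 is about which eye the investigator has to measure. The vessel-ingrowth comparison is about which group a participant belongs to: habitual daily disposable hydrogel wearer, habitual daily disposable silicone hydrogel wearer, or non-wearer. These are different pieces of information, so the reason does not reach this measure.

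Masking is also more practicable here than for a live measurement, because a photograph is stored and can be coded before anyone measures it. As 4.1.3 stands, the images may be read by someone who knows the group and the expected direction.

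Group membership is not randomized, so this comparison is already open to confounding. If reading the images involves judgement, bias towards Hypothesis 1 would be added to that and could not be removed in the analysis.

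**Working it through.** **1. Which images are involved.** Section 2 asks for a three-group comparison of vessel ingrowth at baseline. Group 3 has no visit after Visit 0 (4.7.1), so the comparison must rest on Visit 0 data. This is an inference, because the Visit 0 procedure lists are partly redacted, but Group 3 has no other visit from which images could come.

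**2. What the stated reason covers.** By 4.1.1, 4.7.2 (criterion 9) and 4.8.4, the randomized eye is the one that wears the study lens under closure on Day 2. No study lens is worn at Visit 0.

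**3. Whether knowing the eye reveals the group.** Suppose an eye had already been allocated at Visit 0 and only that eye were read. The reader would need to know right or left. That does not tell the reader whether the participant wears hydrogel, silicone hydrogel or no lenses. The reason fails for this measure on either reading of when the eye is allocated.

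**4. Whether redaction could rescue it.** Parts of 4.1.1, 4.9.2, 4.10 and 4.11 are redacted and may describe how images are taken and measured. Section 4.1.3 is not redacted and makes no exception. If hidden text did provide for masked reading, 4.1.3 would contradict it and would still need correcting.

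**5. What a reader shift would do (illustration only).** The plan gives no reader-bias figure, no SD and no sample size for vessel ingrowth. Its only sample-size figure, a total of 32 in section 11.1, is for hyperemia. It reproduces with a two-sided two-sample t-test at effect size 1.2, power 0.9 and alpha 0.05 (15.62, so 16 per group). It has no bearing on this point.

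Inputs:
- n = 17 per group (4.7.1).
- Significance level 0.05 with no multiplicity adjustment (11.2).
- Assumed: a two-sided two-group t-test, no true difference, and a reader shift of b SD in one group.

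Formulas:
- Degrees of freedom = 2 × 17 − 2 = 32; critical value 2.037.
- Noncentrality = b × √(17/2) = 2.915 × b.
- Total false-positive rate = P(|T| > 2.037), with T noncentral t. The rate in the direction of Hypothesis 1 = P(T > 2.037).

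| Assumed shift (SD) | Noncentrality | Total rate (nominal 5%) | Towards Hypothesis 1 (nominal 2.5%) |
|---|---|---|---|
| 0.1 | 0.29 | 5.9% | 4.7% |
| 0.25 | 0.73 | 10.9% | 10.5% |
| 0.5 | 1.46 | 29.3% | 29.3% |

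A simulation of 200,000 trials per shift gave total rates of 5.9%, 10.8% and 29.2%. A small shift does little. At the larger shifts, almost all the false positives fall on the side the hypothesis predicts.

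**The case against.** The strongest objection is that harm is not shown. Bias needs a human reader who exercises judgement and knows the group, and the visible text says only that photographs undergo image analysis. If that analysis is fully automated, the risk largely disappears. This stands, and it is why the coding step below is conditional. It does not rescue the reason given in 4.1.3.

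Second, the randomized eye may not be only a Day 2 matter. Section 4.1.3 says the main variables are measured in that eye, section 4.7.1 speaks of randomizing participants in every group, and section 14 equates randomization with assigning a study ID. An eye allocation could therefore exist at Visit 0. That is a fair reading, so the conclusion should not rest on timing. It rests on the difference between eye and group, which this reading leaves untouched.

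Third, the error rates have no anchor. The shifts are assumed, and so is the test, since section 11.2 names none for the three-group comparison. This is correct: the table shows what a given bias would do, not that it is likely.

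Fourth, the study openly declares itself non-masked, calls itself initial, and bases its sample size on hyperemia, which this point leaves alone. These facts limit the harm. But disclosure does not make an inapplicable reason apply, and section 11.1 says a trend in the data may be used to plan a larger study.

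Finally, masking would be imperfect and its cost is partly guessed. Both are true and are stated with the fix.

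**Conclusion.** The concern holds. The only reason given for excluding masking does not apply to reading stored images for vessel ingrowth, a primary measure compared between habitual-wear groups. That conclusion rests on unredacted text and on the fact that knowing the eye is not knowing the group.

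The consequence is conditional. It matters to the extent that image measurement involves operator judgement, which the readable text does not settle. No size of bias can be established, and the rates above depend on assumed shifts and an assumed test. Confidence is medium. The change should be made because it is cheap, leaves the sample size as it is, and protects a directional, non-randomized primary comparison.

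**What to change.** In section 4.1.3:

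- Limit the stated reason to measurements made live at the visits.
- Add that, where image measurement involves operator judgement, Visit 0 vessel-ingrowth images are coded so that they carry no group, site or participant ID. Existing staff who do not measure the images would do this. One candidate is the team named in section 4.1.2, where the "randomization schedule will be generated by CORE's Data Management Team"; the plan does not say whether that team can code images, so this needs confirming.
- State that the images are measured by whoever is already planned to do so, before group labels are linked.
- Record the limitations: the photographer remains unmasked; a reader who also examined the participant may recognise an image; and image appearance may reveal the site. Because Group 3 is recruited only at CORE, recognising a Eurolens image would rule out Group 3.

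**Cost.** One wording change and a file-coding task. The number of images is not readable, so assume 1 to 8 per participant and 1 minute each. Participants number 3 × 17 = 51 (target) to 3 × 26 = 78 (maximum). That gives 51 × 1 = 51 to 78 × 8 = 624 images, or 51/60 = 0.85 hours to 624/60 = 10.4 hours. Images may have to be transferred between sites, which is not costed here, and measurement must wait until images are coded, possibly in batches. There is no extra visit or procedure.

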4.2 STATEMENT OF COMPLIANCE

This protocol document has been developed in accordance with the following:

- ISO 14155 Clinical Investigation of Medical Devices for Human Subjects, Parts 1 & 2
- ICH Harmonized Tripartite Guideline for Good Clinical Practice
- The University of Waterloo's Guidelines for Research with Human Participants
- Tri-Council Policy Statement: Ethical Conduct for Research Involving Humans, 2nd Edition. <http://www.pre.ethics.gc.ca/eng/policy-politique/initiatives/tcps2-eptc2/Default/>
- Declaration of Helsinki

4.4 ETHICS REVIEW

This study will be conducted in accordance with Institutional Review Board regulations (U.S. 21CFR Part 56.103) or applicable IEC regulations. Copies of all IRB/IEC correspondence with the investigator/sponsor will be kept on file.

This protocol will be submitted to and reviewed through the Office of Research Ethics (ORE) at the University of Waterloo, Canada and to the respective ORE at the University of Manchester, UK. Notification of ethics clearance of the application is required prior to the commencement of the study at each site. The conduct of this study will be given clearance by the Clinical Research Ethics Committee at the University of Waterloo, Canada, and the respective Research Ethics Committee at the University of Manchester, UK.

4.5 CLINICAL TRIAL REGISTRATION

This study will be registered in the clinical trials registry (<https://clinicaltrials.gov/>) by the study sponsor.

4.6 INFORMED CONSENT

Informed consent shall be obtained in writing from all participants prior to their enrolment in the study, and before any procedure specific to the clinical investigation is carried out. Based on local research ethics requirements, Eurolens Research may use a different terminology for the information consent letter/ICL (participant information sheet (PIS) and informed consent form/ICF).

4.7 STUDY POPULATION

4.7.1 NUMBER OF PARTICIPANTS

Up to a maximum of 26 participants in each study group will be randomized, with a target of completing 17 in each of the three groups.

Groups 1 and 2 will be recruited at both CORE (Canada) and Eurolens (UK). These participants will be exposed to the study contact lens on the second day of the study. There will be competitive recruitment between the two sites and though unlikely, depending on recruitment progress, it is possible that all the subjects will be seen only at CORE (Canada) or only at Eurolens (UK). This means that a maximum of 52 and a minimum of 0 participants will be exposed to the study contact lens at each site.

Group 3, the non-lens wearing group, will all be recruited at CORE (Canada). These participants will only attend the first study visit/day and will not be exposed to the study contact lens.

Participants will be recruited using the study site records and advertising approved by the respective Office of Research Ethics (ORE). Each participant will be given a unique study specific ID number. Additionally, all participants must meet all the study inclusion and none of the exclusion criteria listed below.

4.7.2 INCLUSION AND EXCLUSION CRITERIA

A person is eligible for inclusion in the study if he/she:

1. Is between 17 and 60 years of age inclusive (age matching required between all 3 study groups), and has full legal capacity to volunteer;
2. Has had a self-reported oculo-visual examination in the last two years.
3. Has read and signed an information consent letter;
4. Is willing and able to follow instructions and maintain the appointment schedule;

5. No previous history of overnight contact lens wear or PMMA (polymethylmethacrylate) lens wear.
6. Auto-refraction vertexed spherical equivalent between +4.00 and -8.00 (prescription matching required between groups 1 & 2). This criterion is non-applicable to participants in group 3.
7. Is found to be in one of the study groups matched by age (± 5 years), ethnicity (Asian vs. non-Asian) and CL Rx (± 2.00 D) according using the following criteria:

GROUP 1: For the past (minimum) 6 months has ONLY worn spherical DDSH lenses AND prior to wearing this lens they only wore SH material lenses in the past (minimum) 3 total years.

GROUP 2: For the past (minimum) 6 months has ONLY worn spherical DDH lenses AND prior to wearing this lens they only wore H material lenses in the past (minimum) 3 total years.

GROUP 3: No previous experience of contact lens wear (no need to match Rx of this group).

8. For groups 1 & 2, currently and for at least the previous 6 months has had habitual daily disposable wear schedule of at least 8 hrs a day, 5 days a week in only one material category - either silicone hydrogel or hydrogel material. This criterion is not-applicable to participants in group 3.
9. Is willing to wear the study contact lens in the randomized eye for 3 hours of eye closure on the second study day. This criterion is not-applicable to participants in group 3.
10. Has clear and healthy corneas and anterior eye and no active* ocular disease;
11. Can achieve monocular HCVA of logMAR 0.10 or better in each eye with subjective refraction or pinhole.
12. Can achieve acceptable fit and comfort in the randomized eye with the study lens. This criterion will be confirmed at the baseline visit (V1). This criterion is not-applicable to participants in group 3.
13. Has a wearable pair of spectacles.

A person will be excluded from the study if he/she:

1. Is participating in any concurrent clinical trial;
2. Is unable/unwilling to provide permission for the study site to seek CL history from their eye care practitioner
3. Has any known active* ocular disease and/or infection;

4. Has a systemic condition that in the opinion of the investigator may affect a study measure or interfere with contact lens wear; this may include, but not be limited to, diabetes, hyperthyroidism, recurrent herpes simplex/zoster, Sjogren's syndromes, xerophthalmia, acne rosacea, Stevens-Johnson syndromes, and systemic connective tissue disorders e.g. rheumatoid arthritis.
5. Is using any systemic or topical medications that in the opinion of the investigator may affect a study measure;
6. Has known sensitivity to fluorescein dye, topical anesthetic, or products to be used in the study;
7. Appears to have any active* ocular pathology, ocular anomaly or severe insufficiency of lacrimal secretion (severe dry eye) that would affect the wearing of contact lenses;
8. Appears to have any signs of corneal inflammation or previous infection or corneal opacity/scar;
9. Is pregnant, lactating or planning a pregnancy at the time of enrolment (by verbal confirmation at the screening visit), due to potential ocular physiological changes, such as changes in the corneal shape and cell types;
10. Is aphakic;
11. Has undergone refractive error surgery, or has a history of any ocular surgery or injury.
12. Is a toric or multifocal contact lens wearer.

* For the purposes of this study, active ocular disease is defined as infection or inflammation which requires therapeutic treatment. Mild (i.e. not considered clinically relevant) lid abnormalities (blepharitis, meibomian gland dysfunction, papillae), corneal and conjunctival staining and dry eye are not considered active ocular disease.

Repeated screenings

In some circumstances a repeated screening may need to be scheduled. Examples include, but are not limited to:

1. Incomplete information available at time of screening to determine eligibility (e.g. current lens brands worn, history from current eye care practitioner etc.)
2. Study procedures unable to be completed in time scheduled for visit;
3. Study products not available at the time of the screening visit;

4. A transient health condition which may affect the eye(s) (e.g. a common cold, active allergies, fatigue etc.)
5. The short term use of medications (e.g. antibiotics, antihistamines etc.)
6. Reassessment of baseline ocular conditions (e.g. corneal and/or conjunctival staining, scars etc.)

The maximum total number of screenings permitted will be 3 i.e. 2 repeated screenings are allowed.

4.8 STUDY MATERIALS

4.8.1 LENSES

Details of study lenses are show in Table 1.

Table 1: Lens parameters to be used in this study

Manufacturer	CooperVision
Lens Name	PREFERENCE STANDARD
Material	tetrafilcon A
EWC (%)	43%
Centre thickness (mm) @ +6.00 D	0.26
Dk	9.3
Dk/t (+6.00D)	3.6
BOZR (mm)	8.3
Diameter (mm)	14.0
Sphere power (D)	+6.00 D
CE marking on the label	Yes

The study lens is no longer licensed by Health Canada or marketed in Canada. The investigational testing authorization for this study will be obtained from Health Canada by the study sponsor.

4.8.2 CONTACT LENS CARE SYSTEM

No contact lens care systems will be used in this study. The study lens will inserted directly from sterile saline in the standard lens vial (sealed by the manufacturer).

4.8.3 REWETTING DROPS & SALINE

No rewetting drops will be used in this study. In the event of lens binding a few drops of sterile saline solution may be instilled into the eye to loosen the lens and therefore facilitate safe lens

removal. A log of whether saline was used to aid lens removal will be maintained. Saline solution may also be used to rinse residual sodium fluorescein from the eyes after corneal staining assessment. Worn lenses will be collected from the participants' lens-wearing eye at the end of the 3-hour wearing period (or on discontinuation/exit from the study) and will be disposed as described section 4.8.6 of the protocol.

